8.4.1 Time period and frequency for collecting AE and SAE information

All AEs and SAEs will be collected from the signing of the ICF until the SFU or ETV (if applicable) at the time points specified in the Schedule of Activities (Section 1.3) and must be reported in the ClinBase even if no study intervention was taken but specific study procedures were conducted. This includes all AEs not present before the initial visit and all AEs that recurred or worsened after the initial visit.

All SAEs will be recorded and reported to the UCB Study Physician or designee immediately and under no circumstance should this exceed 24 hours, as indicated in Appendix 3 (Section 10.3). The investigator will submit any updated SAE data to the sponsor within 24 hours of it being available.

Investigators are not obligated to actively seek information on AEs or SAEs after conclusion of the study participation. However, if the investigator learns of any SAE, including a death, at any time after a participant has been discharged from the study, and the investigator considers the event to be reasonably related to the study intervention or study participation, the investigator must promptly notify the sponsor.

The method of recording, evaluating, and assessing causality of AE and SAE and the procedures for completing and transmitting SAE reports are provided in Appendix 3 (Section 10.3).

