9.2.4 Secondary safety endpoints analysis

Secondary safety endpoints in this study are the occurrence of TEAEs, treatment-emergent SAEs, and the occurrence of TEAEs leading to withdrawal from the study.

Unless stated otherwise, all safety analyses will be performed on the SS.

All AEs will be coded using the most recent Medical Dictionary for Regulatory Activities (MedDRA®) and characterized as pre-treatment and treatment-emergent according to the intake of the IMP.

The occurrence and incidence of TEAEs will be summarized by MedDRA system organ class and preferred term and by treatment group. The occurrence and incidence of TEAEs will also be summarized by maximum event intensity and by relationship to the study medication. Adverse events will be categorized by severity (mild/moderate/severe). Adverse events leading to discontinuation and SAEs will also be summarized by treatment group. All AEs will be listed and will include actions taken for each AE, the time of onset of the AE after dosing, and the duration of each AE.

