5.5.2 Adverse Events

An Adverse Event is any untoward medical occurrence in a participant or clinical study participant, temporally associated with the use of study medication, whether considered related to the study medication.

Adverse events with start date/time prior to first treatment are defined as pre-treatment. These events will not be included in any tabulated summaries but will be listed.

Treatment emergent AEs (TEAE) are all AEs starting on or after the date/time of first treatment and up to including 4 days after last treatment, or any unresolved event already present before administration of treatment that worsens in intensity following exposure to the treatment.

AEs with a start date after 4 days of last treatment are defined as post-treatment. These events will not be included in any tabulated summaries but will be listed.

In case of missing or partially missing AE dates, the following rules will apply. Start and stop dates of AEs will be displayed as reported in the participant data listings (ie, no imputed values will be displayed in data listings).

The following rules will be applied for partial start dates and time:

- If only the month and year are specified and the month and year of the first treatment is not the same as the month and year of the start date, then use the 1st of the month, or the date of Screening if this is later (if the imputation results in an end date that is earlier than the start date, then use the 1st of the month). If time is missing, it will be imputed as 00:00 h
- If only the month and year are specified and the month and year of the first treatment is the same as the month and year of the start date, then use the date of the first treatment. If the imputed start date that is after the specified end date, then use the 1st of the month, or the date of Screening if this is later (if the imputation results in an end date that is earlier than the start date, then use the 1st of the month). If the imputed date is the date of treatment then time will be imputed as the start time of the treatment (ie, event will be regarded as treatment emergent)
- If only the year is specified, and the year of the first treatment is not the same as the year of the start date, then January 01 will be used. If time is missing, it will be imputed as 00:00 h

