Adverse events will be assigned to Treatment Periods, based on the onset date/time of the AE. Assignment to Treatment Periods will be done after missing dates have been imputed as described above. AE will be assigned to a treatment based on the treatment received in the Treatment Periods as given in [Table 10](#).

Table 10 AE Treatment Period Assignment

Study	Period	Start	End
UP0152	Treatment Period 1	Start date is on or after administration of treatment in Treatment Period 1	Prior to administration of treatment in Treatment Period 2
	Treatment Period 2	Start date is on or after administration of treatment in Treatment Period 2	Prior to administration of treatment in Treatment Period 3
	Treatment Period 3	Start date is on or after administration of treatment in Treatment Period 3	

The following summaries will be provided by formulation and feeding condition groups:

- Incidence of TEAEs – Overview
- Incidence of TEAEs
- Incidence of Serious TEAEs
- Incidence of TEAEs leading to study discontinuation
- Incidence of TEAEs leading to permanent treatment discontinuation
- Incidence of TEAEs by maximum intensity
- Incidence of TEAEs by relationship to study medication

AEs will be presented as “number of participant (percentage of participant) [number of events]”. In this style of output, “[number of events]” will include all cases of an AE including repeat occurrences in individual participant, while “number of participant” will count each participant only once.

AEs will be presented by system organ class (SOC), high level term (HLT) and preferred term (PT) in a frequency table, giving the number of events, the number of participants, and the percentage of participants who experienced the event. Participants with multiple AEs are only counted once within each PT, each HLT and within each SOC.

Summaries by maximum severity will count each participant at most once within each MedDRA level based on the maximum severity/event intensity within that MedDRA level.

In summaries including intensity, the following intensity categories will be summarized: ‘Mild’, ‘Moderate’, ‘Severe’. Participants who experience the same event multiple times will be included in the most severe category for tabulations by maximum intensity. Events with missing intensity will be considered as ‘Severe’ events for summary purposes but recorded as missing in the listings.

All summaries will be sorted alphabetically by SOC. Within SOC, it will be sorted by decreasing frequency of PT.

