A by-participant listing will be presented for by formulation and feeding condition for all AEs for the SS. This will include reported term, SOC, PT, the onset date/time and outcome date/time

of the event (including relative days), stop date and time (or ongoing, if applicable; relative days), the AE duration, severity, relationship, action taken, and outcome. In addition, the listing will flag TEAEs, Serious TEAEs, and AE of special interest. A glossary of AE terms including reported term, SOC and PT will also be presented.

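### SAP 5.5.2 leaves non-fatal SAEs that start more than 4 days after the last dose out of the serious-event tables, and SAP 6.4 does not declare this narrowing of Protocol 9.2.4

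*SAP*

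**What the plan says.** **Protocol.** Section 8.4.1 sets the collection period: "All AEs and SAEs will be collected from the signing of the ICF until the SFU or ETV". Section 4.1 places SFU 7 days (± 2) after the final dose. Section 9.2.4 says AEs will be "characterized as pre-treatment and treatment-emergent according to the intake of the IMP". It names no post-treatment class and gives treatment-emergent status no end day. It adds: "Adverse events leading to discontinuation and SAEs will also be summarized by treatment group".

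**SAP.** Section 5.5.2 counts an AE as treatment-emergent if it starts between first treatment and a point "up to including 4 days after last treatment". The later class follows: "AEs with a start date after 4 days of last treatment are defined as post-treatment. These events will not be included" in tabulations, although they are listed. The serious-event table in 5.5.2 is "Incidence of Serious TEAEs", and the serious-event tables named in SAP 6.5 are also limited to TEAEs. For the by-participant AE listing, "the listing will flag TEAEs, Serious TEAEs, and AE of special interest". Table 10 assigns an AE to the third period by the rule "Start date is on or after administration of treatment in Treatment Period 3", with no end given. SAP 6.4, the place for changes to protocol-planned analyses, reads as not applicable.

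**The concern.** The protocol's split depends only on drug intake. A new SAE on Day 18 follows intake, so under that split it is treatment-emergent and belongs in the planned SAE summary. The SAP moves it to a class that no AE table may show, and does not record the change.

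Safety and tolerability is the secondary objective, and at most 18 participants are randomized, so one participant with an SAE is 1/18 = 5.6% of the sample. A single omission would visibly change the serious-event table.

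The schedule could produce such an event. Laboratory tests are planned at SFU, and the footnotes to Protocol Table 10-3 make ALT at or above 3 times ULN with INR above 1.5 reportable as an SAE. The potential Hy's Law definition in SAP 6.1.7 requires raised bilirubin. A case found at SFU on INR alone would therefore miss both the serious-event tables and that listing, though it would still be in the general AE listing.

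**Working it through.** **Inputs.** Doses on Days 1, 6 and 11 (SAP 5.1.1.4, Study Periods). SFU on Day 18 ± 2 (Protocol 1.3 and 4.1). TEAE window of 4 days after last treatment (SAP 5.5.2). Half-lives of 11, 10 and 16 h for minzasolmin and its two metabolites (Protocol 4.2).

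**1. Reproduce the plan's own figures.** Relative day = current day − last treatment day + 1. Day 16: 16 − 11 + 1 = 6. Day 20: 20 − 11 + 1 = 10. These match Relative Days +6 to +10 for Safety Follow-Up in SAP Table 4. Maximum duration: 28 + 20 = 48 days, as stated.

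**2. End of the window.** For completers, 11 + 4 = Day 15, which is Relative Day 15 − 11 + 1 = 5, the last day of Washout Period 3. The whole SFU interval falls after it. If the last dose was on Day 1 or Day 6, the window ends on Day 5 or Day 10. The early termination visit has no fixed day, so no length can be given there.

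**3. Follow-up collected but not tabulated, per completer.** The SAP does not say whether 4 days means 96 h or the end of Day 15. The elapsed times below assume dose and SFU visit both at 08:00.

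| SFU day | Calendar days after Day 15 | Share of days from first dose to SFU | Elapsed, 96 h reading | Elapsed, end-of-Day-15 reading |
|---|---|---|---|---|
| 16 | 16 − 15 = 1 | 1/16 = 6% | 1 day | 8 h = 0.33 day |
| 18 (nominal) | 18 − 15 = 3 | 3/18 = 17% | 3 days | 2 d 8 h = 2.33 days |
| 20 | 20 − 15 = 5 | 5/20 = 25% | 5 days | 4 d 8 h = 4.33 days |

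On the 96 h reading, an event late on Day 15 would also count as post-treatment.

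**4. Is the window too short?** 96/11 = 8.7 half-lives for minzasolmin; 96/10 = 9.6 and 96/16 = 6.0 for the metabolites. The protocol's washout argument uses 5 half-lives, at most 5 × 16 = 80 h. The window exceeds that.

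**5. Trace one new non-fatal SAE starting on Day 18 through the plan.**

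| Output or rule | Included? |
|---|---|
| Collection, Protocol 8.4.1 | Yes |
| Treatment-emergent under the two-class split, Protocol 9.2.4 | Yes; no end day is set |
| Serious-event tables, SAP 5.5.2 and 6.5 | No |
| AE listing, SAP 5.5.2 | Yes, but the named seriousness flag covers serious TEAEs only |
| AE of special interest listings, SAP 6.1.7 | Only if potential Hy's Law or hypersensitivity |
| Discontinuation due to AEs, SAP 5.2 | Only if it led to study discontinuation |
| Declared in SAP 6.4 | No |

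**The case against.** The strongest reply is that the protocol never meant all SAEs. Its secondary endpoint is treatment-emergent SAEs, in the endpoint tables, in the opening of 9.2.4 and in SAP Table 1. SAEs are collected from consent, and a pre-treatment SAE has no treatment group in a crossover, so the SAE sentence cannot cover everything collected. This stands: the missing qualifier in that sentence is weak evidence by itself. It does not remove the point, because the protocol gives treatment-emergent status no end day, and the SAP's cut-off narrows the summary on either reading.

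Second, Protocol Section 9 leaves technical detail to the SAP, and an end day can be seen as such detail. That is fair for setting the window. It is a weaker defence for barring later events from every table without a note in 6.4.

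Third, several stronger readings are tempting, and the documents do not support them.

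- A reader might infer that late SAEs are lost. They are listed, and SAP 5.1 calls for listings of all documented data, so seriousness should appear there even without a flag.
- A reader might infer that late liver events go unseen. Cases with raised bilirubin are largely covered by the potential Hy's Law listing, which has no 4-day limit.
- A reader might infer that deaths are omitted. SAP 6.5 has an All Deaths line, although the ban in 5.5.2 makes no exception for it.
- A reader might infer a broken registry commitment. Protocol 10.1.7 promises only TEAEs and treatment-emergent SAEs.
- A reader might take the empty end of Treatment Period 3 in Table 10 for an error. It lets a late event be assigned to the last treatment, which is useful.

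**Conclusion.** The point holds as a gap in tabulation and an undeclared narrowing. Under SAP 5.5.2, a non-fatal SAE starting from Day 16 to SFU in a completer is collected and listed but absent from the serious-event tables. The affected follow-up is 1 to 5 calendar days per completer, 3 at the nominal visit. The documents give no daily event rate, so no count of missed events can be stated. With three single doses in at most 18 healthy participants it is probably very small.

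The conclusion rests on reading the protocol's two-class split as having no end day, which is what the text says. It does not rest on the four-day window being wrong. That window exceeds 5 half-lives for all three compounds and ends with Washout Period 3, so it should stay.

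**What to change.** 1. Tabulate all SAEs, and preferably all AEs, with onset from first dose to SFU or early termination, by last treatment received. Show those after the 4-day window in a separate post-treatment row or table.
2. Make the AE listing flag every SAE, not only serious TEAEs.
3. Record the 4-day window and its rationale in SAP 6.4, state whether it means 96 h or the end of Day 15, and exempt the All Deaths line from the ban on tabulation.

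Leave the TEAE definition as it is, keep Treatment Period 3 in Table 10 open-ended, and add nothing to the registry output on this account. The cost is some SAP wording, one listing flag and one extra, probably near-empty, output. Data collection does not change.

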- If only the year is specified, and the year of the first treatment is the same as the year of the start date, then the date of the first treatment will be used. If this results in an imputed start date that is after the specified end date, then January 01, or the date of Screening if this is later will be used (if the imputation results in an end date that is earlier than the start date, then January 01 will be used). If the imputed date is the date of first treatment then time will be imputed as the start time of the treatment (ie, event will be regarded as treatment emergent)
- If the start date is completely unknown, then use the date of first treatment. If this results in an imputed start date that is after the specified end date, then use January 01 of the year of the end date, or the date of Screening if this is later.

The following rules will be applied for partial stop dates:

- If only the month and year are specified, then use the last day of the month

- If only the year is specified, then use December 31 of the known year
- If the stop date is completely unknown, do not impute the stop date

Missing or partially missing date and/or times will be imputed as described in [Table 9](#) for the calculation of duration of each AE. AE duration is computed and reported in day and time format.

Table 9 Calculation Rules for Duration of AEs

Data Availability	Onset Date/Time	Outcome Date/Time	Calculation Rules
Complete data	D1/T1	D2/T2	Duration = $(D2-D1)*24+(T2-T1)$
End time missing	D1/T1	D2/--	End time is substituted by time 23:59h (=23.98 in decimal format). Duration= $(D2-D1)*24+(23.98-T1)$
Start time missing	D1/--	D2/T2	Onset time is substituted by 00:00h. Duration= $(D2-D1)*24+T2$
Start and end time missing	D1/--	D2/--	Duration= $(D2-D1)*24$
Start day and time missing	--/--	D2/T2	Duration= $(D2-D0)*24+(T2-T0)$ For a participant in the SS, D0 and T0 are the date and time of the first administration of study medication and for screen failures, D0 is the date of the Screening Visit date and T0=00:00h.
End day and time missing	D1/T1	--/--	If the stop date is missing, duration will not be calculated.
Start and end date missing	--/--	--/--	If the stop date is missing, duration will not be calculated.

The duration of each AE will be calculated as follows and will be presented in dd:hh:mm format where dd represent days, hh: hours, and mm: minutes:

$$\text{Duration of AE} = \text{End date/time of AE} - \text{Start date/time of AE} \quad (2)$$

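### AEs imputed to the first dose are attributed to the Period 1 treatment, which is wrong whenever onset followed dose 2 or dose 3

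*SAP*

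**What the plan says.** SAP 5.5.2 Adverse Events sets the start-date rules.

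- Month and year known: where the month of first dosing "is the same as the month and year of the start date, then use the date of the first treatment"; where it "is not the same as the month and year of the start date, then use the 1st of the month" (Screening is used instead when it came later).
- Year only: where the year of first dosing "is the same as the year of the start date, then the date of the first treatment will be used"; where it "is not the same as the year of the start date, then January 01 will be used".
- Nothing known: "If the start date is completely unknown, then use the date of first treatment".

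A known stop date changes the imputed start only when the imputed start would fall after it.

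The order of steps is explicit: "Assignment to Treatment Periods will be done after missing dates have been imputed as described above". Table 10 defines those periods; Period 1 runs from the first dose until the second. An event then takes the treatment of its period: "AE will be assigned to a treatment based on the treatment received in the Treatment Periods". The result feeds every TEAE table: "The following summaries will be provided by formulation and feeding condition groups". Listings show start dates as reported. The SAP plans no flag for imputed attributions and no sensitivity analysis of them.

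**The concern.** In a study with one treatment, moving an undatable AE to the first dose is a conservative way to keep it treatment-emergent. Here each participant takes three treatments, on Days 1, 6 and 11. The imputed date settles two questions: whether the event is a TEAE, and which treatment it is charged to. The first needs a conservative answer. The second has no conservative answer, and the rule always gives Period 1.

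Occurrence of TEAEs is a secondary endpoint, reported by formulation and feeding condition. The hypersensitivity listing (SAP 6.1.7) uses the same grouping, and Protocol 2.3 calls hypersensitivity an important identified risk. In a study of 18 people, one event in the wrong column is visible. Each treatment comes first in two of the six sequences, so no treatment is favoured on average, but a real difference between treatments would be blurred.

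**Working it through.** The plan gives no figure on this point, so there is none to reproduce.

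**Inputs.** Doses on Days 1, 6 and 11 (SAP, Study Periods). Sequences ABC, BCA, CAB, ACB, BAC, CBA (Protocol Table 4-1, SAP Table 2). TEAE window to 4 days after the last dose, that is Day 15 (SAP 5.5.2). 18 randomized (Protocol 9.4).

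**Step 1: events imputed to the first dose.** Compare the Period 1 treatment with the treatment of the period in which the event truly began. They agree in 6 of 6 sequences if the true period is 1, in 0 of 6 if it is 2, and in 0 of 6 if it is 3. With p1, p2, p3 the shares of such events that truly began in each period:

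accuracy = p1 × 6/6 + p2 × 0/6 + p3 × 0/6 = p1

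| p1 / p2 / p3 | Accuracy |
|---|---|
| even thirds | 33.3% |
| 50 / 25 / 25 | 50% |
| 60 / 20 / 20 | 60% |
| 20 / 30 / 50 | 20% |
| 0 / 0 / 100 | 0% |

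The documents give no onset distribution, so these rows show a range and are not estimates. Example: in sequence ABC, an event that began on Day 12 and is recorded by month only, in the month of first dosing, is imputed to Day 1 and tabulated under A. The treatment that preceded it was C.

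**Step 2: the full date rules over a calendar.** Assumptions, not from the documents: dosing at 08:00, onset uniform by the hour from first dose to the end of Day 15, and first dose on each of 365 days from 1 September 2024.

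| What is known of the start | Imputed to first dose | Attribution correct overall | Wrong among events after dose 3 |
|---|---|---|---|
| nothing | 100% | 34.1% | 100% |
| year only | 98.0% | 34.5% | 99.4% |
| month and year | 76.5% | 39.0% | 93.0% |

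The 34.1% is 120/352: Period 1 has 120 of the 352 hours in the window.

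**Step 3: dates in a month other than that of first dosing.** These go to the 1st of the month, and the result depends on the calendar.

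- Doses on 20, 25 and 30 October, onset 2 November, recorded as November: imputed to 1 November, Period 3, correct.
- Doses on 28 October, 2 and 7 November, onset 9 November, recorded as November: imputed to 1 November, Period 1, wrong.

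**Step 4: events that truly began on Days 16 to 20.** With a complete date these are post-treatment and only listed. With month and year only, under the Step 2 calendar, equal weight per day and noon onset, 44.1% are imputed to the first dose and become tabulated Period 1 TEAEs. The remainder go to the 1st of a later month: 16.4% fall in Period 1, 16.4% in Period 2, 13.2% in Period 3, and 9.9% stay post-treatment (total 100%).

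**Step 5: size in a table.** With 18 participants in a column, one participant is 1/18 = 5.6 percentage points. This is a maximum. SAP 5.5.2 counts a participant once per preferred term, high level term and system organ class, so a participant already counted there does not move the column.

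**The case against.** The strongest reply is that the rule will hardly ever be used. Participants stay in the clinic for all three periods and are discharged on Day 15. AE review is scheduled in every column of the Schedule of Activities, including the follow-up visit on Day 18 ± 2. A start date known only to the month would be unusual, even for an event between discharge and follow-up. The TEAE tables are descriptive, and the hypotheses in SAP section 2 concern PK only. Affected events can also be recognised in the listings: start dates appear as reported, and the relative day of a partial date prints as dashes. All of this stands, and it makes the point minor. It does not make the rule right for the events it does reach, and the tables themselves would carry no sign of it.

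A reader might infer more than the documents support:

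- *Every partial start date goes to the first dose.* It does not. Dates in another month or year follow separate rules (Step 3).
- *Attribution is no better than chance.* It equals one third only if onsets are even across periods, and the documents do not say that they are.
- *Events after the third dose are always misassigned.* That is exact for wholly unknown dates and for any event actually imputed to the first dose. It fails for some month-and-year or year-only dates, as the October example shows.
- *A dosing-day AE with no time falls to the previous treatment, because a missing start time becomes 00:00.* Table 9 introduces that substitution for calculating duration. The cross-reference in the period-assignment sentence is loose, but the SAP does not say that 00:00 is used for assignment.

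**Conclusion.** The point holds within limits. The stated rule sends an AE whose start is known only to the month or year of first dosing, or not at all, to the Period 1 treatment. The attribution is wrong whenever the event began after dose 2 or dose 3. That conclusion needs no assumption about onset, only that no participant receives the same treatment twice. How often it is wrong does depend on onset: accuracy is the share that truly began in Period 1. A true post-treatment event with a partial date can also enter the tables as a Period 1 TEAE; the 44% for month-and-year dates rests on the calendar assumptions in Steps 2 and 4.

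The practical effect is probably small, at most 5.6 points in a column per affected participant with 18 per column. This is a cheap improvement and no threat to the study's conclusions.

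**What to change.** Separate the two decisions in SAP 5.5.2.

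1. Keep the first-dose imputation, but use it only to decide whether the event is a TEAE.
2. For treatment attribution, bound the onset by the known date parts, the stop date, the last AE review without the event and the first AE review that records it.
3. If one dose is compatible with those bounds, assign the event to that treatment.
4. If more than one remains compatible, count it once under each compatible treatment and flag it in the table footnote and the listing.
5. State that the 00:00 substitution in Table 9 applies to duration and is not used for period assignment. This is a clarification of wording only.

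Under these rules an event first reported after discharge, and absent at the Day 15 review, stays in the tables but moves to the Period 3 treatment.

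The cost is a paragraph of SAP text and a few lines of programming on data already collected. The drawback is that an undatable event appears in more than one column, which slightly inflates incidence and dilutes differences between treatments; the flag lets a reader see where.
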